5.3 Interim Analysis and Stopping Guidelines

There will be no planned interim analyses for efficacy or futility for this trial, while safety will be monitored using stopping guidelines as described below.

Monitoring of two key safety endpoints (overall mortality by 100 days post-HCT, graft failure by 100 days post-HCT) will be conducted, and if either rate significantly exceeds pre-set thresholds, the NHLBI will be notified in order that the DSMB can be advised. Policies and composition of the DSMB are described in the BMT CTN's Manual of Procedures. These stopping guidelines serve as triggers for consultation with the DSMB for additional review and are not formal "stopping rules" that mandate automatic closure of study enrollment. The number of enrolled patients that fail to receive transplant using Treosulfan and the occurrence of toxicity, adverse events, and other safety endpoints will be monitored and reported to the DSMB annually, at a minimum; in the event that any safety concerns arise, these data will be conveyed to the DSMB expeditiously.

Monitoring rule for overall mortality by 100 days post-HCT:

Monitoring will be performed beginning when at least 3 patients are evaluable for the monitoring rule (died or been followed for at least 100 days post-HCT), until enrollment is closed. At least three deaths must be observed, along with crossing of a stopping boundary as described below, in order to trigger referral to the DSMB for further review. The expected probability of mortality within 100 days is expected to be no more than 15%. The null hypothesis that the 100-day mortality rate is less than or equal to 15% is tested. An extension of the sequential probability ratio test (SPRT) for censored exponential data will be used for monitoring, as described in greater detail below and in **Appendix I**. This SPRT is based on testing the null hypothesis that the 100-day mortality rate is less than or equal to 15%. The sequential testing procedure conserves type I error at 5% across all of the assessments and can be represented graphically. At each interim analysis, the total time on study (e.g., in months or years, x axis) is plotted against the total number of endpoints (e.g., patients experiencing death, y axis). The continuation region of the SPRT is defined by two parallel lines. Only the upper boundary will be used for monitoring to protect against excessive 100-day mortality. If the graph falls above the upper boundary, the SPRT rejects the null hypothesis, and concludes that there are more events than predicted by the observed time on study. Otherwise, the SPRT continues until enrollment is closed.

This procedure assumes a censored exponential distribution for the time until death during the first 100 days, and censor's follow-up time after 100 days. Only deaths that occur on or before the patient has been followed for 100 days are counted. Total time on study is computed as time from transplant to death, or to 100 days, whichever comes first, summed for all patients on study.

The usual measures of performance of an SPRT are the error probabilities α and β of rejecting H_0 when $\theta = \theta_0$ and of accepting H_1 when $\theta = \theta_1$, respectively, and the expected sample size $E(N|\theta_i)$. The test to be used in this protocol were developed from an SPRT contrasting 15% versus 35% 100-day rate of mortality, resulting in decision boundaries with a common slope of 0.084 and an upper intercept of 2.424, with nominal type I and II errors of 8% and 15%, respectively.

The actual operating characteristics of the truncated tests, shown in **Table 16**, were determined in a simulation study that assumed uniform accrual of 40 patients over a four-year time period, exponential time to failure after HCT, and implemented monthly monitoring of the SPRT. In

practical implementation, however, the SPRT is monitored monthly and also reviewed each time a new event occurs to identify any crossing of a toxicity boundary in between monthly assessments.

TABLE 16: OPERATING CHARACTERISTICS OF SEQUENTIAL TESTING PROCEDURE FOR DAY 100 MORTALITY FROM A SIMULATION STUDY WITH 10,000 REPLICATIONS			
True 100-Day Rate	15%	25%	35%
Probability Reject Null	0.052	0.427	0.855
Mean Month Stopped	49.7	39.7	25.3
Mean # Endpoints in 100 Days	5.8	7.8	7.0
Mean # Patients Enrolled	38.8	31.7	21.0

For example, the testing procedure for 100-day mortality rejects the null hypothesis in favor of the alternative 5.2% of the time when the true 100-day mortality rate is 15%, and 85.5% of the time when the rate is 35%. This corresponds to a type I error rate of $\alpha = 0.052$ and a type II error rate of $\beta = 0.145$. When the true 100-day mortality rate is 35%, on average, the DSMB will be consulted 25.3 months after opening, when 7.0 events have been observed in 21.0 patients.

Monitoring rule for graft failure by 100 days post-HCT

Graft failure is expected to be no higher than 10% by 100 days. Graft failure within 100 days will be monitored using a sequential probability ratio test (SPRT) for binary data that compares a rate of 10% under the null hypothesis to a rate of 30% under the alternative hypothesis. This sequential testing procedure preserves the type I error rate at a prespecified level across all of the monthly examinations. The binary SPRT can be represented graphically by plotting the number of evaluable patients against the cumulative number of events. The continuation region of the SPRT is defined by two parallel lines. Only the upper boundary will be used for monitoring in order to protect against excessive Day 100 graft failure rates. If the cumulative number of graft failures falls above the upper boundary the SPRT rejects the null hypothesis and concludes that more graft failures occurred than should be expected in the observed number of evaluable patients. Otherwise, the SPRT continues until enrollment reaches the target sample size of 40 patients. The binary SPRT can be displayed in a tabular form, as shown in **Table 17**. This table gives the rejection boundaries for the number of Day 100 graft failure events corresponding to the number of evaluable patients. At least three graft failures must be observed in order to trigger review.

This procedure considers only graft failures occurring by Day 100. A binary SPRT contrasting 10% versus 30% Day 100 graft failure rates results in decision boundaries with a common slope of 0.1862 and an upper intercept of 1.7984 with nominal type I and II error rates of 7.5% and 15%, respectively. Because the SPRT employed here is truncated at a sample size of 40 and only uses the upper decision boundary, the actual type I and II errors will vary from these nominal levels.

Table 17: Sequential Monitoring Plan based on Binary SPRT for Graft failure by day 100

Number of Evaluable Patients	Rejection Boundary for # of graft failures by day 100
3-6	3
7-11	4
12-17	5
18-22	6
23-27	7
28-33	8
34-38	9
39-40	10

The actual operating characteristics of the truncated test are shown in **Table 18**, obtained from a simulation study that assumed uniform accrual of 40 patients over a 48-month period. This simulation study implemented monitoring of the SPRT after each additional patient became evaluable. In practical implementation, however, the SPRT is monitored monthly and also reviewed each time a new event occurs to identify any crossing of a toxicity boundary in between monthly assessments.

Table 18: Operating Characteristics of the Binary SPRT for Day 100 graft failure from a Simulation Study with 10,000 Replicates

True Day 100 Graft Failure Rate	10%	20%	25%	30%
Probability Reject Null	0.052	0.484	0.736	0.898
Mean Month Stopped	49.6	37.8	30.0	23.0
Mean # events by Day 100	3.9	5.8	5.7	5.1
Mean # Patients Enrolled	38.7	29.1	22.7	17.0

The testing procedure rejects the null hypothesis in favor of the alternative 5.2% of the time when the true Day 100 graft failure rate is 10% and 89.8% of the time when the rate is 30%. This corresponds to a type I error rate of 5.2% and a type II error rate of 10.2%. If the true Day 100 graft failure rate is 30%, the DSMB will be consulted 23 months after opening on average, when 5.1 events have been observed in 17 patients.

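### Section 5.3 ends both safety rules when enrollment ends, but Tables 16 to 18 describe monitoring to the last patient's day 100, and Table 18 labels evaluable patients as enrolled

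*Protocol*

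**What the plan says.** All of this is in Protocol Section 5.3.

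**Mortality rule.** "Monitoring will be performed beginning when at least 3 patients are evaluable for the monitoring rule", and the same sentence runs the monitoring only to enrollment closure. A patient is evaluable after death or 100 days of follow-up. The paragraph closes: "Otherwise, the SPRT continues until enrollment is closed". The boundary comes from an "SPRT contrasting 15% versus 35% 100-day rate of mortality", giving a "common slope of 0.084 and an upper intercept of 2.424, with nominal type I and II errors of 8% and 15%, respectively". Table 16 comes from a "simulation study that assumed uniform accrual of 40 patients over a four-year time period" with monthly looks. At a true rate of 15% it gives a rejection probability of 0.052 and a mean stopping month of 49.7.

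**Graft-failure rule.** If the boundary is not crossed: "Otherwise, the SPRT continues until enrollment reaches the target sample size of 40 patients". Table 17 lists boundaries up to 39-40 evaluable patients, and the text says the test is truncated at a sample size of 40. Evaluable is not defined for this rule. For Table 18, "This simulation study implemented monitoring of the SPRT after each additional patient became evaluable", again with 40 patients over 48 months. At a true rate of 10% it gives 0.052 and month 49.6. At 30% it gives month 23.0, 5.1 events and 17.0 patients, in a row labelled as enrolled.

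For both rules the protocol adds that in practice "the SPRT is monitored monthly and also reviewed each time a new event occurs to identify any crossing".

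**The concern.** These are the only two formal safety boundaries in the trial, and Tables 16 and 18 tell the DSMB how they behave. If the text and the tables describe different rules, whoever runs the monitoring must choose one. Following the text switches both triggers off before the last patients treated have passed the 100-day window that the rules are about. It also leaves the last row of Table 17 with normally no use.

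The row label in Table 18 matters for a related reason. A DSMB member comparing the two tables would take both bottom rows as the number of patients enrolled when the DSMB is consulted. For graft failure that number is understated.

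**Working it through.** **Inputs.** 40 patients over 48 months; 100 days = 100/30.44 = 3.29 months; boundaries, hypotheses and nominal errors from Section 5.3; formulas for the exponential test from Appendix I.

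**1. Reproduce the boundaries.**
- Mortality: θ0 = -ln(0.85)/3.285 = 0.0495 and θ1 = -ln(0.65)/3.285 = 0.1311 per month, so ln(θ1/θ0) = 0.975. Slope = (0.1311 - 0.0495)/0.975 = 0.0838. Intercept = ln(0.85/0.08)/0.975 = 2.424. Both agree with the protocol.
- Graft failure: denominator ln[(0.3 × 0.9)/(0.1 × 0.7)] = 1.350. Slope = ln(0.9/0.7)/1.350 = 0.1862. Intercept = ln(0.85/0.075)/1.350 = 1.7984. Both agree, and every row of Table 17 follows from them.

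**2. Compare stopping months with the written end.** If monitoring ends by month 48, no trial stops later, so the mean cannot exceed 48. The stated null means are 49.7 and 49.6. The last patient's day 100 falls at 48 + 3.29 = 51.3 months. In Table 16, taking about 25 months for the 5.2% of trials that trigger (an assumption), trials that never trigger must end at (49.7 - 0.052 × 25)/0.948 = 51.1 months.

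**3. Simulate both ends.** Mortality: 100,000 trials per setting, monthly looks. Graft failure: 40,000 trials per setting, failures counted at day 100. Ranges cover evenly spaced and random uniform accrual.

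| | Stated | To last patient's day 100 | To closure |
|---|---|---|---|
| Mortality, null mean month | 49.7 | 48.5-49.6 | 46.5 |
| Graft failure, null mean month | 49.6 | 48.5-49.7 | 46.5-46.6 |
| Mortality, P(reject) at 15% | 0.052 | 0.054-0.055 | 0.053-0.054 |
| Mortality, P(reject) at 25% | 0.427 | 0.423-0.428 | 0.413-0.415 |
| Mortality, P(reject) at 35% | 0.855 | 0.862-0.865 | 0.850-0.852 |

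For graft failure, an exact recursion to 40 evaluable patients gives 0.052, 0.485, 0.741 and 0.902 at 10, 20, 25 and 30%, against 0.052, 0.484, 0.736 and 0.898 in Table 18. Truncating at 37 evaluable patients gives 0.051, 0.469 and 0.888 at 10, 20 and 30%.

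**4. Patients still pending at closure.** 3.29 × 40/48 = 2.7. About 37 are evaluable, so the 39-40 row of Table 17 is normally not reached.

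**5. Bottom row of Table 18.** Events divided by the row: 3.9/38.7 = 0.10; 5.8/29.1 = 0.20; 5.7/22.7 = 0.25; 5.1/17.0 = 0.30. Each ratio equals the true rate, as it must when the denominator is patients with a completed outcome. The exact mean evaluable at 30% is 16.9. Enrollment by month 23.0 is 23.0 × 40/48 = 19.2, and simulation gives 18.6-19.2. In Table 16 the same check gives 25.3 × 40/48 = 21.1 against 21.0, so that row really is enrolled.

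**6. When a graft failure enters the count.** With failures entered at day 100, the null trigger probability is 0.051-0.052 (0.050-0.051 ending at closure). With failures entered when they occur and known at day 42 (an assumption; Section 3.2.2 uses day 42 for primary failure), it is 0.062 with evenly spaced accrual and 0.072 with random accrual. Under that second rule only about 17 patients are enrolled at 30%.

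**7. Event-time looks, mortality.** Type I error becomes 0.058-0.059. Ending at closure, power at 35% is 0.856-0.859 with 19.5-19.9 enrolled.

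**The case against.** Several points on the other side are sound.

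- **The look schedule is disclosed.** A reader might infer that the error rates are invalid because the simulations did not look at each event. Section 5.3 says so openly after both tables, and the effect on mortality is about half a percentage point. This is a stated approximation.
- **The last patients are not unmonitored.** Section 5.1.2 follows them for 12 months. Sections 4.3.5 and 4.3.6.4 require prompt entry of deaths and expedited reporting of unexpected serious events, and Section 5.3 sends safety data to the DSMB at least annually, sooner if concerns arise. Only the two sequential triggers lapse. Section 4.3.5 lets the DSMB advise on continuing accrual, and after closure there is none to stop. Ending at closure could therefore be a deliberate choice, but it is not the choice the tables describe.
- **The graft-failure text can be read as running to 40 evaluable patients**, given the truncation at 40 and Table 17. That is probably what was meant, but the closing sentence says enrollment.
- **A false-trigger rate of 6-7% for graft failure is not established.** It needs failures to count on occurrence, which the protocol neither states nor excludes. It also cannot be combined with the figure of about 19 enrolled, which belongs to counting at day 100.
- **Patient counts are not understated throughout.** The mortality rule as written enrolls slightly fewer than Table 16 states.
- **Rejection probabilities alone do not identify the simulated end.** At 35% mortality the stated 0.855 lies between the two versions. The stopping months decide it.

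**Conclusion.** The contradiction holds and needs no simulation to establish: a mean of 49.7 or 49.6 months cannot arise from rules that end by month 48. The tables fit monitoring to the last patient's day 100. The mislabelled row in Table 18 also holds, on the table's own ratios.

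The size is modest. As written, the triggers lapse for about 2.7 of 40 patients and lose 1 to 2 percentage points of trigger probability; type I error stays near 5%. At 30% graft failure the number enrolled is understated by about 2. These results assume the protocol's accrual of 40 patients over 48 months, exponential death times within 100 days, and graft failures counted at day 100. The boundaries prompt DSMB consultation and do not mandate stopping. Sample size and primary analysis are unaffected.

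**What to change.** 1. Replace both closing sentences, and the matching phrase in the opening sentence of the mortality rule, so that monitoring runs until the last enrolled patient has had the event or reached day 100. The tables already simulate this, so no new simulation is needed. Both triggers stay active about 3.3 months longer.
2. Relabel the bottom row of Table 18 as mean evaluable patients, change the sentence below the table to 17 evaluable patients, and add a row for patients enrolled (about 19 at 30%).
3. Define evaluable for graft failure. Either enter each failure with that patient's day-100 evaluation, which keeps the type I error near 5%, or count it on occurrence and restate the type I error (about 6-7% if failures are known at day 42) together with the patient counts. The second option needs one re-run of the simulation.
4. Re-simulating the mortality rule with event-time looks is optional, since it moves the type I error only from 0.052 to about 0.058.

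Items 1 and 2 cost an edit to Section 5.3 and one additional output from the existing simulation.

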5.4 Demographic and Baseline Characteristics

Demographic and baseline characteristics will be summarized for all patients. Characteristics to be examined may include:

- a. Patient factors:
 - Genetic mutation (if known)
 - Age at diagnosis
 - Age at transplantation
 - Race/Ethnicity

- Gender
 - Karnofsky/Lansky Performance status
 - Indication(s) for transplant
 - Baseline ferritin and hepatic/cardiac iron level if known
 - Disease specific baseline characteristics:
 - Diamond Blackfan anemia – history of steroids (Yes/No)
 - Shwachman-Diamond syndrome
 - PNH – history of eculizumab or other PNH specific therapy (Yes/No)
- b. Transplant factors:
- Hematopoietic cell source (BM and PBSC)
 - Donor type (HLA-matched related, HLA-matched unrelated, mismatched unrelated)
 - Cell dose infused: Total nucleated cell (TNC) per kg recipient body weight, CD34 count per kg recipient body weight, and/or CD3 count per kg recipient body weight

5.5 Analysis Populations and General Analysis Guidelines

5.5.1 Primary Analysis Population

All patients conditioned with a Treosulfan-containing regimen will be included in the primary analysis population. Time to event analyses will start at initiation of conditioning (day -6 of transplant). Analyses for the primary endpoint, all secondary endpoints, and safety endpoints, will use the primary analysis population. The primary analysis will occur once all patients have been followed for 12 months, Endpoint Review Committee adjudication completed, and data is locked.

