[name] and colleagues at the Fred Hutchinson Cancer Research Center have been leading a phase II prospective study using Treosulfan-based conditioning in patients with non-malignant diseases including 23 patients with BMFD (NCT00919503). Outcomes of the first 14 patients are published.¹² Conditioning consisted of Treosulfan (14 grams/m², days -6 to -4; total dose 42 grams/m²), fludarabine (30 mg/m²/day, days -6 to -2; total dose 150 mg/m²), +/- rabbit ATG (thymoglobulin; 1 mg/kg/day, day -4, 2.5 mg/kg days -3 and -2; total dose 6 mg/kg; n=20) followed by HLA-matched sibling (n=5) or HLA-matched unrelated donor (URD) (n=15) bone marrow (BM, n=16), peripheral blood stem cell (PBSC, n=5), or sibling BM plus sibling cord blood (n=2) grafts. Three patients received a single class 1 allele (n=2) or DQB1 antigen (n=1) mismatched graft. GVHD prophylaxis consisted of tacrolimus and methotrexate (MTX). Outcomes were encouraging. With a median follow-up of 2 years, the 2-year overall survival (OS) and event-free survival (EFS) were both 96%. The 1-year GVHD-free, EFS was 87%. The median time to neutrophil recovery was 22 (range, 13-26) days. The median time to platelet recovery defined as a platelet count >50,000 without platelet transfusions x 7 days was 24 (range, 13-82) days. The cumulative incidences of grades II-IV and III-IV acute GVHD at day 100 and NIH chronic GVHD at 1 year were 39%, 4% and 9%, respectively. None of the patients experienced graft rejection, with 22 patients having full (≥95%) and one patient having stable mixed donor CD33 myeloid engraftment.

These primarily single center results indicate that the combination of Treosulfan, fludarabine, and rabbit anti-thymocyte globulin (ATG) is effective at establishing donor engraftment with low toxicity and excellent survival in patients with BMFD. Preliminary data from this trial provides strong support for a multi-center prospective clinical trial. Therefore, the primary objective of this clinical trial is to evaluate the 1-year GVHD-free, EFS in patients with BMFD undergoing HCT using Treosulfan-based conditioning in a multi-center prospective clinical trial.

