3.2 Secondary Endpoints

3.2.1 Overall Survival

Overall survival will be estimated at day 100, 6 months, and 1 year after HCT.

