3.2.2 Event-Free Survival

Event-free survival will be estimated at 12 months after HCT. Grade III-IV acute GVHD and chronic GVHD requiring systemic immune suppression will be considered in this estimate.^{61,62} An event is defined as death due to any cause, primary or secondary graft failure/rejection, or 2nd HCT whichever occurs first.

Primary Graft Failure/Rejection: defined as never achieving ANC $\geq 500/\mu\text{L}$ or never achieving $\geq 5\%$ donor myeloid chimerism assessed by peripheral blood chimerism assays by day +42 post-HCT. Second infusion of hematopoietic cells is also considered indicative of primary graft failure by day +42 post-HCT.

Secondary Graft Failure/Rejection: defined as $< 5\%$ donor myeloid chimerism in peripheral blood beyond day +42 post-HCT in patients with prior documentation of hematopoietic recovery with $\geq 5\%$ donor cells by day +42 post-HCT. Second infusion of hematopoietic cells is also considered indicative of secondary graft failure.

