14. Echocardiogram/MUGA: Echocardiogram or MUGA for assessment of left ventricular ejection fraction (LV EF) or, for patients unable to obtain LV EF, LV shortening fraction (LVSF; within 3 months of study enrollment)
15. Pulmonary function testing (PFT): to include FEV1, FVC, FEV1/FVC, TLC, RV, and DLCO (corrected for hemoglobin). For patients who are unable to perform PFTs due to age or developmental delay, pulse oximetry is an acceptable alternative.
16. Assessment for hepatic or cardiac iron overload:

Table 13: Patient Clinical Assessments/Testing

- a. Formal assessment of hepatic and/or cardiac iron overload within 6 months of study enrollment using a validated methodology such as T2* MRI (liver and heart), ferriscan (liver), or biopsy (liver) per institutional practice.
 - i. For patients ≥ 18 years with a history of significant transfusions defined as ≥ 8 packed red blood cell transfusions per year for ≥ 1 year or have received ≥ 20 packed red blood cell transfusions (lifetime cumulative) will require formal hepatic and cardiac iron measurement. In addition, patients with a prior history of hepatic or cardiac iron overload will also require formal assessment for hepatic and cardiac iron overload.
 - ii. For patients < 18 years old with a history of significant transfusions defined as ≥ 8 packed red blood cell transfusions per year for ≥ 1 year or have received ≥ 20 packed red blood cell transfusions (lifetime cumulative) will require formal hepatic iron measurement. In addition, patients with a prior history of hepatic iron overload will also require formal assessment for hepatic iron overload.
 - b. Day +365: Follow-up assessment for hepatic and potentially cardiac iron overload is recommended for patients with a history of iron overload pre-HCT or those considered at risk for iron overload post-HCT per institutional practice.
17. Bone marrow aspirate and biopsy for pathology, flow cytometry, cytogenetics, and MDS FISH panel. The MDS FISH panel should evaluate for deletion 5q/monosomy 5, monosomy 7/deletion 7q, trisomy 8, and deletion 20q
 - a. Baseline (within 60 days prior to enrollment)
 - b. Day +365: Per the discretion of the treating physician a bone marrow evaluation around 1-year post-HCT.
 18. GVHD assessments: Patients should be assessed weekly until Day +100 post-HCT for GVHD. After Day +100, patients will be assessed at each follow-up visit through 12 months for the presence of GVHD.

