5.1.4 Primary Endpoint

The primary endpoint of the trial is GVHD-free, EFS (GEFS) at 1-year post-HCT using Treosulfan-based conditioning. Events contributing to this endpoint are specified in Section 3.1. The primary objective of this trial is to estimate the 1-year GEFS probability, using the Kaplan Meier method, along with 95% confidence intervals.

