5.7.5 Acute GVHD

Cumulative incidence of acute grade II-IV GVHD will be estimated using the cumulative incidence function, treating death prior to acute GVHD as a competing risk. Point estimates and confidence intervals will be provided for the cumulative incidence at day 100 and day 180 post-HCT, using the complementary log-log transformation. Time to GVHD will be calculated from transplant date. Cumulative incidence of acute grade III-IV GVHD will be estimated using the cumulative incidence function, treating death prior to acute GVHD as a competing risk. Point estimates and confidence intervals will be provided for the cumulative incidence at day 100 and day 180 post-HCT.

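### Section 5.5.1 starts all time-to-event clocks at conditioning, but the endpoints sit at post-HCT landmarks; the main effect is on Day 28 neutrophil recovery

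*Protocol*

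**What the plan says.** Protocol Section 5.5.1 defines the population as everyone conditioned with treosulfan and sets the origin: "Time to event analyses will start at initiation of conditioning (day -6 of transplant").

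Elsewhere the protocol counts from transplant:

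- Section 5.1.4: "The primary endpoint of the trial is GVHD-free, EFS (GEFS) at 1-year post-HCT using Treosulfan-based conditioning".
- Section 3.2.1: "Overall survival will be estimated at day 100, 6 months, and 1 year after HCT".
- Section 3.2.2: "Event-free survival will be estimated at 12 months after HCT".
- Section 3.2.3 places neutrophil recovery at day 28 and platelet recovery at day 100, both after HCT. Sections 3.2.6, 3.2.9 and 3.2.10 likewise place chronic GVHD, EBV and CMV at post-HCT times.
- Section 5.7.5: "Time to GVHD will be calculated from transplant date".
- Section 5.3, mortality rule: "Total time on study is computed as time from transplant to death, or to 100 days, whichever comes first".

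Sections 5.6 (GEFS), 5.7.1 (OS) and 5.7.3 (hematologic recovery) give 1 year, Day 28 or Day 100 without naming an origin, so the general rule in 5.5.1 governs them as written. Visits in Table 12 are scheduled in post-HCT days, with the 12-month visit at 365 ± 28. The notes to Tables 1 and 12 allow extra rest days before infusion and keep the day the infusion finishes as Day 0.

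**The concern.** Two programmers who follow this protocol faithfully could produce different results for the same patients. One would run the Kaplan-Meier and cumulative incidence clocks from conditioning, as 5.5.1 instructs. The other would run them from transplant, as the endpoint definitions imply. GEFS itself combines GVHD, which 5.7.5 times from transplant, with death and graft failure, which 5.5.1 times from conditioning.

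The gap between the clocks is not a constant that can be subtracted afterwards. It is six days by plan and longer for any patient given extra rest days. A landmark measured from conditioning therefore falls on different post-HCT days in different patients.

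At stake are the meaning of the Day 28 neutrophil figure, which would be hard to compare with its own definition, and an unambiguous time origin for the primary endpoint.

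**Working it through.** **Landmark shift.** Post-HCT day = analysis day − 6, with the six-day gap of the planned schedule:

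| Label in the analysis section | Post-HCT day on the 5.5.1 clock |
|---|---|
| Day 28 | 28 − 6 = 22 |
| Day 100 | 100 − 6 = 94 |
| Day 180 | 180 − 6 = 174 |
| 1 year | 365 − 6 = 359 |

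With k added rest days, each result is k days earlier.

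**Neutrophil recovery.** Section 1.2 reports for the earlier cohort of 23 patients: "The median time to neutrophil recovery was 22 (range, 13-26) days". Assume those days count from transplant; the protocol does not say so.

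- On the 5.5.1 clock, Day 28 is post-HCT day 22, which is the median. About 50% have recovered.
- On the Section 3.2.3 definition, post-HCT day 28 lies beyond the longest time observed (26). All have recovered, so 100%.

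The damage is confined to the Day 28 landmark. Day 100 (post-HCT day 94) lies well beyond the range. So does the day 42 used for neutrophils in the objectives, which becomes post-HCT day 36.

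**The plan's own GEFS figure.** Table 15 reproduces with exact binomial limits at n=40: 38/40 gives 83.1-99.4%, 36/40 gives 76.3-97.2%, 34/40 gives 70.2-94.3% and 32/40 gives 64.4-91.0%. The table is not in dispute.

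**GEFS, constant hazard (assumption).** Moving the landmark from post-HCT day 365 to 359 changes S to S^(359/365).

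- At the earlier cohort's 87% (Section 1.2): 0.87^(359/365) = 0.872, a shift of 0.2 points.
- At the registry's 65% (Section 1.3.2): 0.65^(359/365) = 0.655, a shift of 0.5 points.

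**GEFS, events dated to the 12-month visit.** Table 13, note 18 says: "After Day +100, patients will be assessed at each follow-up visit through 12 months for the presence of GVHD". In Table 12 the only such visits are day 180 and day 365. An on-target 12-month visit is analysis day 365 + 6 = 371, six days past the landmark. Of the 57 days in the window (337-393), 34 lie after post-HCT day 359, 1 on it and 22 before it.

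Assume visits are spread evenly over the window. The share after the landmark is:

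- conditioning origin: (393 − 359)/56 = 0.607
- transplant origin: (393 − 365)/56 = 0.500
- due to the origin: 0.607 − 0.500 = 0.107

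Take chronic GVHD at 9% (Section 1.2), and assume that one third to all of it is first recorded at this visit with no earlier onset date, so 3-9% of patients.

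| | 3% | 9% |
|---|---|---|
| Excluded, conditioning origin | 1.8 points | 5.5 points |
| Excluded, transplant origin | 1.5 points | 4.5 points |
| Due to the origin | 0.3 points | 1.0 point |

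**One patient.** With n=40 each excluded event is 1/40 = 2.5 points. For example, 34/40 (70.2-94.3%) becomes 35/40 = 87.5% (73.2-95.8%).

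**The case against.** A conditioning origin has a rationale. It matches a population of all conditioned patients and keeps deaths before infusion as events. Section 5.5.1 also labels time in transplant days, so it can be read as starting risk at day −6 while leaving the landmarks at post-HCT days. On that reading nothing moves. This is a fair account of what may have been intended, but the text does not say it: 5.5.1 makes no exception for landmarks, and 5.7.5 would not need its own origin if transplant time were understood throughout. The rationale can also be kept with a day 0 origin.

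It is also true that Section 1.2 states no origin for the earlier cohort's recovery times, so the 50% against 100% contrast is conditional.

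Three stronger readings are tempting, and the documents do not support them.

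- **GEFS is inflated by several points.** A reader might take the 1.8-5.5 points above as the effect of the origin. Most of that comes from the ±28-day visit window and remains with a transplant origin. It also requires that onset is never back-dated. Section 3.2.6 draws chronic GVHD data from providers and charts and records systemic therapy, and 5.5.1 requires endpoint adjudication before analysis. If these date onset properly, the effect is near zero. Nor does the suggested taper in 2.5.3.1.4 imply clustering at 12 months: 10% a week from day 180 ends near day 250, before the window opens at day 337.
- **Pre-infusion deaths escape safety monitoring.** The person-time formula in 5.3 does start at transplant. But the same section treats a patient who has died as evaluable, and separately reports to the DSMB the number of enrolled patients not transplanted. The text is not explicit enough to say that such deaths are never counted.
- **The 5.3 rule should move to conditioning time.** That would recreate two clocks and depart from the simulation behind Table 16, which times failure from HCT.

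**Conclusion.** The contradiction is real and lies in the protocol's own text: one general rule starts time at conditioning, while the time-to-event endpoints, the GVHD analysis and the mortality rule use transplant. A statistical analysis plan might settle it, but it would have to overrule one of these statements.

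The consequence is large for one secondary result. Applied literally, Day 28 neutrophil recovery is read at post-HCT day 22, and the same patients could show about 50% rather than 100% recovered. This assumes that the earlier cohort's distribution applies and was counted from transplant.

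For GEFS the origin alone matters little: about 0.2 points at 87% under a constant hazard, and 0.3-1.0 point under evenly spread visits with 3-9% of patients first recorded as having chronic GVHD at 12 months. The exposure that remains is any event dated only to an on-target 12-month visit, which would fall outside the estimate at 2.5 points per patient. The documents do not show that GEFS is materially biased.

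**What to change.** In Section 5.5.1, replace the origin sentence with a statement that:

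1. time is measured from day 0 (HCT) for all time-to-event endpoints;
2. all patients conditioned with a treosulfan-containing regimen stay in the analysis population;
3. a death between the start of conditioning and infusion counts as an event at day 0.

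Then delete the origin sentence in 5.7.5, which becomes redundant. Leave the monitoring clock in 5.3 on transplant time, so that its boundaries and simulated operating characteristics still apply.

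How to date an event first seen at the 12-month visit is a separate question, because the window straddles the landmark under either origin. It can be held in the statistical analysis plan or an adjudication charter.

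The cost is wording only. The programming must retain event times of zero. Estimated GEFS may be very slightly lower.
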